## Ethical issues

**Ethical approval.** The proposal, information sheet, consent form, measures and intervention exercises for the current study will be sent to the University of Sheffield Department of Psychology Research Ethics Sub-Committee for approval through the online ethics application system. In addition, the University of Sheffield's research governance procedure will be followed, including completion of the 'Risk Assessment Checklist for University Sponsored Human-Interventional Studies' and public registration of the study on 'ClinicalTrials.gov'.

**Informed consent.** All potential participants will read an information sheet (see Appendix A) and complete a consent form (see Appendix B) online prior to taking part in the study. They will have the opportunity to ask the researcher any questions about their participation in the study via email. The researcher's email address will be provided on the information sheet.

**Participant withdrawal.** Participants will be able to withdraw from the study at any point until their data are anonymised. Participants will be informed of this on the information sheet and may contact the researcher by email to request that their data is destroyed should they subsequently wish to withdraw from the study.

Eight of the guided self-help emails will be automatically sent from Qualtrics based on completion of the baseline measures. If any participants contact the researcher to withdraw from the study, that participant's Qualtrics data will be exported (for ITT analyses) and then the participant's contact details will be deleted from Qualtrics so that further automatic emails are not sent to that participant.

**Adverse effects.** As with all psychological interventions, there is a risk that taking part in this study may raise participants' awareness of pre-existing distressing thoughts and feelings, leading to some distress during or after taking part in the study. Participants will be made aware of this possibility prior to taking part in the study via the information sheet (see Appendix A). The information sheet will also provide participants with signposting information for mental health support (e.g. the Samaritans) and advise them to speak to their GP if necessary. In addition, if

participants advise the researcher of any adverse effects via email, the researcher will be able to re-iterate options for further support as appropriate. The researcher previously worked in primary care mental health services for five years, providing guided self-help to people with depression and anxiety disorders, and is therefore experienced in dealing with emotional distress and signposting appropriately. If necessary, the researcher will discuss concerns with her primary supervisor, who is a clinical psychologist.

**Confidentiality.** Participants will be informed that their data will be kept confidential and that they will not be personally identifiable in any results of the study. Unique identification numbers will be used throughout the data sets. A data file will be created to contain participants' details and their identification numbers, for matching up quantitative data over time and to allow the destruction of data should participants wish to withdraw from the study. This data file will be password-protected and kept separately from the rest of the participants' data.

Spreadsheets containing participants' names and email addresses will also be created in order to administer the study—for sending emails on the correct dates and tracking participants' logins. No sensitive quantitative data will be kept in these spreadsheets, only dates. These spreadsheets will also be password-protected and kept separately from outcome measures and feedback data. Once data collection is complete, participants' names and email addresses will be replaced with their unique identification numbers.

Participants will be required to log into the study website solely to track user logins for the purpose of monitoring participants' engagement with the intervention from week to week. Participants will log into the website with a username (usually their first name) and password that has been allocated to them by the researcher.

Participants will not be asked to provide any data via the study website, nor will they be able to access any other participants' details. No-one except the researchers involved in the study will have access to participants' contact details.

**Data protection.** Personally identifiable digital data will be stored securely as described above, on the lead researcher's university filestore. The lead researcher will be

the only person with administrator access to the study website. The study website is hosted on the University of Sheffield's servers, and therefore participants' contact details (names and email addresses used to administer user memberships) that are visible to the administrator on the study website will also be stored securely within the university's firewalls. Administrator access to the website is protected by requiring the administrator to log in from within the University of Sheffield's virtual private network (VPN) and uses two factor authentication, requiring a code accessed from the administrator's mobile phone. Wordfence, a Wordpress security plugin, is also being used to provide protection from brute force attacks (malicious attempts to gain access using repeated guesses at user names and passwords) on the frontend of the website. Participants will be made aware of how their data will be protected in the information sheet (see Appendix A).

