## **Acceptability and feasibility criteria**

Acceptability of intervention overall: The percentage of eligible participants who access the webpages will be calculated using Qualtrics data and user logins to the website. The intervention will be considered acceptable if at least 66% of eligible participants log into the website during their sixth week of the study. This criterion was chosen as a recent meta-analysis of computerised CBT for depression and anxiety disorders reported a median retention rate of 66% (Andrews et al., 2018).

Feasibility of providing online self-help: All eligible participants should be able to access the website, so if less than 90% of eligible participants log into the website during their first week of the study, this may suggest that there were problems with accessing the self-help website. This criterion was chosen as more than one in ten people having

difficulty accessing the website is analogous to experiencing a ‘very common’ side effect of a medication (NHS, 2018). User logins for subsequent weeks of the intervention will also be recorded.

Feasibility of providing guidance: Researcher time spent providing email guidance will be recorded, and will be considered feasible if this takes 120 minutes or less per patient over the study period. This criterion is derived from guidance on individual guided self-help interventions for people with depression, which typically consist of up to 240 minutes overall (up to eight sessions at 30 minutes each; NICE, 2010; National IAPT Programme, n.d.): if providing email guidance takes over half the amount of time needed for individual guided self-help programmes, then it cannot reasonably be argued to be “limited facilitation” (NICE, 2010, p. 23). The percentage of participants who requested additional support via email will also be recorded. These figures will inform future trials and implementation of guided self-help for people with skin conditions within health services.

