## Procedure

Data will be collected using Qualtrics, an online survey provider. In the study advert, participants will be provided with a link to the Qualtrics survey page, where they will read the participant information sheet and complete an online consent form (see Appendices A and B). Screening questions relating to the exclusion criteria will be asked before participants complete the demographic questions, clinical information, and baseline measures (see Appendices C–H). Baseline DASS depression scores will be calculated automatically by Qualtrics. Any participants who disagree with the consent statement or who are ineligible for the study will be re-directed to an ‘end of study’ webpage. This will explain that they are not able to continue with the study and recommend that they contact their GP if they need further support. Signposting information about mental health resources and emotional support for skin conditions will also be provided to all participants.

Qualtrics will notify the lead researcher when an eligible participant has completed the baseline survey. Eligible participants will be registered as users on the study website by the researcher and then sent an email with their login details and a link to the study website, with instructions to access the first session of the intervention. Anyone that attempts to access the intervention webpages without logging in will be redirected to the login page—the only exceptions to this are the homepage and the contact page. Requiring participants to log in means that engagement with the intervention can be monitored without involving any third parties for website traffic statistics (for example, Google Analytics), and also means that each participant’s use of the website can be accurately tracked no matter what devices they use. At the end of the first session, participants will be asked to provide feedback on the first session, which will be collected using Qualtrics. Participants will receive an automated email three days after completing the baseline measures to remind them to practise the homework exercise (or go through the session if they haven’t already done so). One

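### Does the plan leave it open whether a withdrawing participant's data are kept for ITT or destroyed, and whether that person still counts as eligible?

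*Combined protocol and SAP*

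**What the plan says.** The Participant withdrawal paragraphs under Ethical issues set out the right to withdraw: "Participants will be able to withdraw from the study at any point until their data are anonymised". A participant "may contact the researcher by email to request that their data is destroyed should they subsequently wish to withdraw from the study".

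The next paragraph deals with the automatic emails. It opens "If any participants contact the researcher to withdraw from the study" and provides that the participant's "Qualtrics data will be exported (for ITT analyses"), after which the contact details are removed from Qualtrics so that no more emails go out.

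Under Confidentiality, the data sets carry identification numbers. A separate file links numbers to people, partly to match data over time and partly "to allow the destruction of data should participants wish to withdraw from the study". Once data collection is complete, participants' "names and email addresses will be replaced with their unique identification numbers".

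The login criteria are under Acceptability and feasibility criteria: "The percentage of eligible participants who access the webpages will be calculated using Qualtrics data and user logins to the website". The intervention counts as acceptable if at least 66% of eligible participants log in during week 6. Fewer than 90% logging in during week 1 may point to access problems. Procedure shows when eligibility is settled: "Qualtrics will notify the lead researcher when an eligible participant has completed the baseline survey". The Data analysis strategy names ITT and completer analyses without defining either set.

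**The concern.** Two instructions attach to one event, an email asking to withdraw. One allows destruction of the data. The other exports the data of any participant who withdraws, makes no exception for a destruction request, and names only contact details as deleted. Read literally, a researcher could keep data that the participant had asked to have destroyed. Nor does any sentence say that a copy already exported is destroyed too.

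The login percentages draw on Qualtrics data and website logins, and a full destruction request could reach both. If the analyst then left that person out of the denominator, a result near 66% or 90% could cross the line in either direction. Readers could not tell unless deletions were reported. The ITT set would shrink in the same way.

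**Working it through.** **Sample size range.** Under Sample size, the minimum of 12 with 48% attrition gives 12/(1 − 0.48) = 23.08, which the protocol states as 23. The maximum is 9 × 60/10 = 54. Both figures reproduce, so N runs from 23 to 54 (32 values).

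**Effect of dropping one person from a login percentage.** Let m be the smallest count with m/N at or above the threshold. Dropping a non-login from a result of m − 1 out of N gives (m − 1)/(N − 1). Dropping a login from m out of N gives the same fraction.

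| Criterion | Dropped | Before | After |
|---|---|---|---|
| Week 6, 66% | a non-login | 15/23 = 65.2% | 15/22 = 68.2% |
| Week 6, 66% | a login | 16/24 = 66.7% | 15/23 = 65.2% |
| Week 1, 90% | a non-login | 20/23 = 87.0% | 20/22 = 90.9% |
| Week 1, 90% | a login | 27/30 = 90.0% | 26/29 = 89.7% |

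Over the 32 values of N, a result one login short is lifted over the line at 21 (66%) and 29 (90%). A result that just passes falls below it at 11 (66%) and 3 (90%). These are counts of sample sizes at which a flip is arithmetically possible. They are not probabilities.

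**Effect on the ITT effect size.** The protocol names no rule for missing follow-up, so assume 12 completers with change scores of mean 0.64 and SD 1, plus k people with zero change. The 0.64 is the meta-analytic d quoted in the introduction, borrowed here only as a completer d_z. With N = 12 + k:

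- mean = 12 × 0.64/N = 7.68/N
- sum of squares = 11 × 1 + 12 × 0.64² = 15.915
- variance = (15.915 − N × mean²)/(N − 1)
- d_z = mean/√variance

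Results:

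- k = 11, N = 23: 0.334/0.779 = 0.43
- k = 10, N = 22 (one deleted): 0.349/0.794 = 0.44
- k = 8, N = 20 (three deleted): 0.384/0.826 = 0.46 (0.465 to three decimals)

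With a completer d_z of 0.4 or 0.8, one deletion moves the ITT value from 0.284 to 0.290, or from 0.511 to 0.525.

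**Do the passages lead to that dropped record?**

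1. *Export against destruction.* The first paragraph covers a person who asks for destruction. The second is about stopping emails, and export comes first so that removing contact details does not lose ITT data. A specific request displaces a default, so both paragraphs can be followed.
2. *Exported copies.* Coded data sets and a linking file kept partly for destruction mean that a participant's rows can be found and removed.
3. *Denominator.* Eligibility depends on the inclusion and exclusion criteria and the baseline DASS depression score, and it is known before registration on the website. Later withdrawal does not alter it, and no passage takes withdrawers out.
4. *Login records.* Login dates are tracked in spreadsheets held apart from outcome data. The protocol does not say what happens to them on a destruction request, but a count of how many people were eligible does not depend on keeping anyone's questionnaire data.

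The percentages in the table therefore describe a step that the protocol never prescribes.

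**The case for a change.** The best case for a change is that keep by default, destroy on request is an inference. The export sentence covers any participant who withdraws, without exception. Data once destroyed cannot be restored, so a rule is best written before the first request arrives. Requests may also come late, because withdrawal stays open until anonymisation and names are replaced only after data collection ends. The point touches participants' rights as well as counting, and a sentence or two would settle it.

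Some of this stands. No supplied sentence ranks the two instructions or says that a deleted person stays counted, and stating both would do no harm. However, the sentence would only record what a sensible analyst would do anyway. The timing argument is weaker than it looks: the replacement of names follows the description of the administrative spreadsheets, and the protocol does not equate that step with anonymisation. The information sheet, which is to inform participants about withdrawal, is not in the supplied text and may already draw the distinction.

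A fuller remedy, such as keeping each deleted person's week-by-week login line, would go further than the problem. It would retain individual data after a destruction request in a sample of 23 to 54, and would itself need ethics review.

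**Conclusion.** The wording is incomplete, but no change to the plan follows. Followed as written, it keeps data by default, destroys them on request, and calculates both login percentages over everyone eligible at baseline, which gives the intended figures.

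A changed result on a login criterion needs three things together: a destruction request, a record dropped from the denominator against the natural reading, and a result within one login of the threshold (for a single deletion). The documents give no frequency for any of these. The 90% criterion is in any case only a signal of possible access problems. On the ITT side, one deletion in 23 moves the illustrative d_z by about 0.01, assuming 12 completers with d_z 0.64 and no change in the other 11.

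The conclusion rests on reading eligibility as fixed at baseline and a destruction request as overriding the default export. Both readings fit every supplied passage. This is a gap that analysts fill sensibly.

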week after completing the baseline measures participants will receive an automated email inviting them to access the second session of the intervention. Automated emails will continue to be sent in this way, with homework reminders and links to subsequent sessions. The emails will also invite the participant to contact the researcher if they require further support with the self-help materials. The researcher will respond to any such emails individually. One week after the last session participants will be invited to provide feedback via Qualtrics about the guided self-help intervention overall, and to complete the outcome measures again.

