### **Data analysis strategy**

Text responses from participants' feedback on the intervention overall will be analysed using content analysis to identify helpful aspects of the intervention and areas for improvement.

Quantitative data (outcome measures and acceptability ratings) will be screened for outliers and missing values, and descriptive statistics will be conducted for all variables. The data will be tested for the assumption of normality. Paired t-tests will be used to test for differences in participants' psychological outcome measures before and after the intervention. This information will also be used to calculate effect sizes ( $d_z$ ) for changes in scores on each outcome measure. Intention-to-treat and completer analyses will be carried out.

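### The plan does not separate stopping the self-help from leaving the study, so someone who announces they are stopping has no written route to the post-intervention measures

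*Combined protocol and SAP*

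**What the plan says.** Ethical issues, Participant withdrawal, sets out what happens when someone writes in to leave: "If any participants contact the researcher to withdraw from the study, that participant's Qualtrics data will be exported (for ITT analyses"), after which "the participant's contact details will be deleted from Qualtrics so that further automatic emails are not sent to that participant". The same paragraph says what the Qualtrics contact record is used for: "Eight of the guided self-help emails will be automatically sent from Qualtrics based on completion of the baseline measures". The eight emails are not listed. The section also lets participants ask for their data to be destroyed, which is a separate matter and adds no other way of stopping.

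The Procedure describes the weekly messages ("Automated emails will continue to be sent in this way, with homework reminders and links to subsequent sessions") and then the end-of-study contact: "One week after the last session participants will be invited to provide feedback via Qualtrics about the guided self-help intervention overall", together with a repeat of the outcome measures. That invitation depends on no level of engagement, and the sending route is not stated.

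The Data analysis strategy specifies paired t-tests and effect sizes for the change in each outcome, and adds "Intention-to-treat and completer analyses will be carried out". It gives no rule for a missing post-intervention score.

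Under Confidentiality, a second contact record is described: "Spreadsheets containing participants' names and email addresses will also be created in order to administer the study", in part "for sending emails on the correct dates and tracking participants' logins".

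**The concern.** A participant can be finished with the programme and still be willing to fill in one last questionnaire. The plan has no step for that person. The only procedure on paper for someone who writes in is full withdrawal, with the record exported and the Qualtrics contact removed. Someone who simply stops logging in stays on the list and is invited to the outcome survey. Follow-up then depends on how a person stops, not on whether they would have answered.

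Two outputs are exposed. The Aims ask for effect-size estimates to inform later research, and they count explicit feedback as part of acceptability. Overall feedback, including the adapted Friends and Family item, is collected only at the end. People who take the trouble to say they are stopping plausibly include those who found the materials unhelpful, and the Sample size section says the acceptability data will guide further development. With a minimum of 12 participants providing data, a few recoverable responses matter.

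**Working it through.** **1. The exit procedure, section by section.**
- Participant withdrawal: data exported, Qualtrics contact deleted. No later collection step.
- Procedure: outcome survey one week after the last session, with no engagement condition. Silent dropouts are covered.
- Data analysis strategy: ITT and completer sets, paired t-tests, no rule for missing post scores.
- None of these sections, nor Estimated timescale, separates stopping the sessions from leaving the study.

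A person handled under the withdrawal paragraph before follow-up has baseline scores and any weekly feedback in the export, but no post score. A paired t-test cannot use that record without an imputation rule.

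**2. Does deletion itself cancel the outcome invitation?** There are six sessions. Assume one homework reminder in each of six weeks and one automated invitation for each of sessions 2 to 6 (the first login email follows registration by the researcher).
- Reminders plus session invitations: 6 + 5 = 11.
- With the outcome invitation: 11 + 1 = 12.
- Stated as sent automatically from Qualtrics: 8.
- Left for another route: 11 − 8 = 3, or 12 − 8 = 4 if the outcome invitation is counted.

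The documents do not show that the outcome invitation is among the eight. The gap is the absence of any written step for inviting a declared stopper, whichever system sends the email.

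**3. The plan's own attrition figures.** Inputs from Sample size: minimum 12, attrition 48%, recruit 23, maximum 54.
- 12 / (1 − 0.48) = 23.08, stated as 23. (Rounding up would give 24; 23 × 0.52 = 11.96.)
- Maximum: 9 × 60 / 10 = 54, as stated.
- Expected post scores: 23 × 0.52 = 11.96, and 54 × 0.52 = 28.08.
- Expected losses: 23 × 0.48 = 11.04, and 54 × 0.48 = 25.92.

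**4. What an outcome invitation could recover.** The documents do not split attrition into announced and silent. Assume that a share w of the losses is announced and that a fraction r of those people would reply if invited. Post scores = N × 0.52 + N × 0.48 × w × r.

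| N | w | r | Post scores |
|---|---|---|---|
| 23 | 0 | any | 11.96 |
| 23 | 0.10 | 0.25 | 11.96 + 0.28 = 12.24 |
| 23 | 0.50 | 0.50 | 11.96 + 2.76 = 14.72 |
| 54 | 0 | any | 28.08 |
| 54 | 0.10 | 0.25 | 28.08 + 0.65 = 28.73 |
| 54 | 0.50 | 0.50 | 28.08 + 6.48 = 34.56 |

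For scale, the half-width of a 95% confidence interval for a mean change, in SDs of the change, is t(0.975, n−1)/√n. This is 0.64 at n = 12 and 0.55 at n = 15.

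**5. Bias.** If stayers change by m and declared stoppers by d, and stoppers are a share w of the sample, analysing stayers alone overstates the mean change by w(m − d). The documents supply none of these three values, so no percentage can be attached. Even in an assumed case an invitation removes only part of the bias. Take m = 4, d = 0, w = 0.25, with every stayer providing a post score. The whole-sample mean is 3.0 and stayers alone show 4.0. If a quarter of stoppers reply, the observed mean is 3.0 / (0.75 + 0.0625) = 3.69. The overstatement falls from 33% to 23%.

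**The case against.** The strongest reply is that the withdrawal paragraph applies to people who withdraw from the study. Estimated timescale defines time in the study as seven weeks, including the follow-up, so ending contact honours the request. Silent dropouts have made no such request, and inviting them is consistent. This stands for anyone who truly wants to leave. It does not help the person who only wants to stop the sessions, about whom the plan is silent and for whom it offers no other procedure.

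A reader might go further and infer any of the following, none of which the documents support.
- That the deleted record carries the outcome invitation. The eight emails are not itemised and appear to be fewer than the emails described.
- That deletion removes the only means of contact. The researcher's spreadsheets hold names and email addresses and are used for sending emails.
- That no withdrawer can ever have a post score. Withdrawal is allowed until data are anonymised, and data are exported before deletion, so someone who withdraws after follow-up can have one. Weekly ratings and comments already given are exported too.
- That the reported change would be overstated by some stated percentage. Any such figure rests on assumed withdrawal rates and effects, and charging all of it to this step also assumes that every stopper would have replied.

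The information sheet was not among the pages available, so its wording on stopping cannot be judged.

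**Conclusion.** The point holds as a gap in the exit procedure. The plan has one written route for people who announce they are stopping, and it includes no offer of the post-intervention measures or overall feedback. A declared stopper who leaves before follow-up would probably enter the ITT set without a post score, and the effect sizes and overall feedback may lean towards those who stayed.

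The size cannot be derived from the documents. Under the assumed ranges the recoverable gain is about 0.3 to 2.8 paired scores with 23 recruited and 0.6 to 6.5 with 54. It is zero if nobody withdraws explicitly or nobody replies. The study's formal criteria do not move: the 66% and 90% thresholds rest on website logins, and the 120-minute limit on researcher time. This is a cheap improvement, not a flaw that undermines the study.

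**What to change.** Reply to a withdrawal email with two options, worded so that neither is pressed on the participant:
- (a) stop the session and reminder emails but still receive the single end-of-study survey on its scheduled date;
- (b) leave the study entirely, with contact details deleted as now.

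Under (a), send the survey from Qualtrics with the other emails cancelled, or from the researcher's spreadsheet if the Qualtrics contact has been deleted. State in the Procedure which system sends the outcome invitation. Amend the withdrawal paragraph and, if needed, the information sheet. Report how many people chose each option, and say in the Data analysis strategy how the ITT analysis treats post scores that remain missing.

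The cost is a few sentences of protocol wording and one template reply. The only burden on participants is one further email, sent only to those who choose (a).
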